### 6.1.8. Tipping Point Analysis

An additional sensitivity analysis using the tipping-point approach will be conducted to assess the robustness of the primary analysis approach. If it is plausible that, for the active treatment group, the distribution of missing primary endpoint responses has a smaller expected reduction than that of the corresponding distribution of the observed primary endpoint responses, the conclusion under the MAR assumption should be examined. It is desired to impose a fixed and definite set of quantities to encapsulate the change in efficacy associated with withdrawal (missing) for the active treatment group, and independently for the placebo group. The tipping point multiple imputation analysis as described by Ratitch et al. (2013) will be applied. Tipping point analysis is a means of exploring the influence of missingness on the overall conclusion from statistical inference by positing a wide spectrum of specifications regarding the missingness mechanism (from less pessimistic to more pessimistic). The analysis finds a (tipping) point in this spectrum of specifications, at which conclusions change from being favorable to the experimental treatment to being neutral. The analysis will be based on the following procedure:

1. The missing data are filled in  $m$  ( $m = 10$ ) times to generate  $m$  complete data sets assuming that we do not differentiate missing data category (similar to assuming the algorithm for missing category 2).
2. The  $m$  complete data sets are analyzed by using standard procedures.
3. The results from the  $m$  complete data sets are combined for the inference.

4. Repeat the steps #1 to generate multiple imputed data sets, with a specified shift parameter that adjust the imputed values for observations in the relevant treatment group independently.
5. Repeat the step 2 for the imputed data sets with shift parameter applied.
6. Repeat the step 3 to obtain the p-value to see if the p-value is still  $\leq 0.05$ .
7. Repeat the steps 4-6 with more stringent shift parameter applied until the p-value  $> 0.05$ .

After such a tipping point is determined, clinical judgment can be applied as to the plausibility of the specifications underlying this tipping point. The tipping point can be identified while the result is no longer statistically significant. This imputation analysis uses a specified sequence of shift parameters, which adjust the imputed values for observations in the active treatment group and independently for the placebo group. A sample of SAS code for sensitivity analysis using the tipping-point method is provided in Appendix 3.

## 6.2. Secondary Efficacy Endpoints

The secondary efficacy endpoints (see [Section 1.1.2](#)) are designed to evaluate the efficacy of volixibat versus placebo for the treatment of pruritus in participants with ICP as well as composite perinatal outcomes.

1. The secondary efficacy endpoint for pruritus is defined as the mean change from baseline to Week 3 in the weekly average worst daily itch score as measured by the Adult ItchRO. The worst daily itch score is averaged over the 7 days preceding baseline and over the 7 days preceding each week through Week 3. If more than 3 days of assessments are missing from a given week, then that weekly average will be set to missing. The analysis of the Adult ItchRO will use an MMRM with a comparable model to that for the primary endpoint.
2. The secondary efficacy endpoint for composite perinatal outcomes is defined as the proportion of participants that experience any of the 4 outcomes specified in [Section 1.1.2](#). For this responder-type endpoint, the number and proportion of participants that are considered a “responder” will be summarized by treatment group at Week 3 and analyzed using a stratified Cochran-Mantel-Haenszel (CMH) test to calculate the p-value for the difference between treatment groups. The p-value from the CMH test will be the basis of the hypothesis testing.

Additionally, the baseline stratum weighted difference in the response rate ( $P_1 - P_2$ ) and its 95% CI will be calculated based on stratum-adjusted Mantel-Haenszel (MH) proportions as described as follows (Koch 1989), where stratification factors include gestational age, baseline ItchRO score, and gestational diabetes:

$$P_1 - P_2 \pm Z_{(1-\alpha/2)} * SE(P_1 - P_2)$$

where

- $(P_1 - P_2) = \frac{\sum w_h d_h}{\sum w_h}$  is the stratum-adjusted MH proportion difference, where  $d_h = p_{1h} - p_{2h}$  is the difference in the response rate between treatment groups 1 and 2 in stratum  $h$  ( $h=1$  to  $12$ ).
- $w_h = \frac{n_{1h}n_{2h}}{n_{1h}+n_{2h}}$  is the weight based on the harmonic mean of the sample size per treatment group for each stratum where  $n_{1h}$  and  $n_{2h}$  are the sample sizes of the treatment groups 1 and 2 in stratum  $h$ .
- $SE(P_1 - P_2) = \sqrt{\frac{\sum w_h^2 \left[ \frac{p_{1h}^*(1-p_{1h}^*)}{n_{1h}-1} + \frac{p_{2h}^*(1-p_{2h}^*)}{n_{2h}-1} \right]}{(\sum w_h)^2}}$ , where  $p_{1h}^* = \frac{m_{1h}+0.5}{n_{1h}+1}$  and  $p_{2h}^* = \frac{m_{2h}+0.5}{n_{2h}+1}$ .  $m_{1h}$  and  $m_{2h}$  are the number of participants who are “responders” in treatment groups 1 and 2 in stratum  $h$ .
- $\alpha = 0.05$
- $Z_{(1-\alpha/2)} = Z_{0.975} = 1.95996$  is the 97.5th percentile of the normal distribution

Note that if the computed lower confidence bound is less than -1, the lower bound is defined as -1. Similarly, if the computed upper confidence bound is greater than 1, the upper bound is defined as 1. Furthermore, as supportive analyses, a Logistic Regression (LR) estimator approach (Ge et al. 2011), as well as a logistic regression model with baseline sBA, gestational age, and presence/absence of gestational diabetes as covariates will be run. The model assumptions of the logistic regression model are not considered a concern because a randomized study has comparable distributions of the treatment groups for covariates and factors for stratification, although they may impact the interpretation of estimated parameters for the covariates. Most importantly, a logistic regression model addresses estimands that are conditional on the covariates in the model, with these estimands sometimes being called participant-specific, and express the extent of efficacy of a treatment that a participant might expect on the basis of her covariates, although they tend to be further from the null for an effective treatment than population average estimand. A randomization-based version of logistic regression will also be considered. It is robust to model assumptions and it has a population average estimand that is the same as the unadjusted odds ratio for comparing two treatments (Zink and Koch 2012).

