In summary, although symptoms are transient for the mother, ICP is associated with increased maternal morbidity, increased risk of life-threatening or even fatal sequelae for the fetus, and chronically debilitating consequences for surviving infants. This is reflected in the widespread policies to manage severe cases of ICP by elective early delivery between 36- and 38-weeks' gestational age or earlier to reduce the risk of late stillbirth and alleviate maternal symptoms. This practice is not evidence based (EASL 2009; Tran et al. 2016; Bicocca et al. 2018; ACOG 2019) and is associated with potentially severe and/or chronic sequela.

The current study is designed to assess the potential of volixibat to reduce maternal pruritus and fetal morbidity and mortality associated with ICP, which would provide a significant efficacy benefit over currently utilized therapies. In ICP, lowering of (or mitigating potential further increases in) maternal sBA would be expected to ameliorate the increased risk of adverse perinatal outcomes associated with increased sBA levels by promoting restoration of the physiologic transplacental gradient and alleviating the accumulation of toxic bile acids in the fetus. Given the evidence supporting the role of elevated sBA as a driver of adverse perinatal outcomes, the mean change in total maternal sBA concentration has been selected as the primary endpoint as a surrogate for clinically relevant perinatal outcomes. Perinatal outcomes will also be directly assessed using a composite measure as a key secondary efficacy endpoint.

The current study design is divided into 2 parts. Part 1 is an open-label phase that provides real-time assessments of safety/tolerability of volixibat 20 mg and 80 mg as well as data for dose exploration and selection for Part 2 of the study. Part 2 is a randomized, double-blind, placebo-controlled phase for confirmatory analysis comparing the selected volixibat dose with placebo for superior efficacy.

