This study assesses the primary efficacy endpoint at 3 weeks because it is clinically relevant as a timeframe within which demonstrated efficacy of a drug for ICP will be important for clinical decision making. In a large population-based, case-control study (Geenes et al. 2014), 669 patients with a singleton pregnancy were identified within the UK Obstetric Surveillance System (UKOSS) as having severe ICP; the mean gestational age was 33 weeks 4 days at time of diagnosis in these patients. Additionally, in a recent double-blind, multicenter, randomized placebo-controlled study that enrolled 605 women with ICP in the United Kingdom (Chappell et al. 2019), the median gestational age was 34.4 weeks at randomization. With the mean/median gestational ages at diagnosis occurring between 33 and 34 weeks—and with Royal College of Obstetricians and Gynaecologists (RCOG) guidelines (2011) recommending consideration of elective delivery for patients with ICP after 37 weeks based on sBA-related risks of stillbirth—approximately 3 weeks of study drug treatment corresponds to a timeframe within which demonstration of sBA reduction is expected to be impactful for clinical decision making. Furthermore, based on clinical experience with another IBAT inhibitor (maralixibat),

continued improvements in sBA are likely to be seen with relatively longer treatment durations, arguing against analysis of sBA prior to the 3-week timeframe as a primary efficacy endpoint. In Study LUM001-501, decreases in both sBA and ItchRO (observer) were observed at Week 2 and continued to decline even further at Week 4 in pediatric participants with non-truncating PFIC2, supporting the benefit of treatment durations >2 weeks for reduction of sBA and pruritus. However, given the mean/median gestational ages for ICP diagnosis (33–34 weeks), along with the requirement for randomization no later than 36 weeks 0 days in Part 2, participants are relatively more likely to be at the upper range of gestational age eligibility in this study, and as such, relatively few participants in this study will be expected to remain on treatment beyond 3 weeks.

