### 3.3. Strata and Covariates

Participants will be randomly assigned to treatment groups via the interactive voice or web response system (IXRS).

- For the primary cohort, a dynamic allocation method, introduced by Pocock and Simon (1975) will be adopted to balance participant assignment between treatment arms based on the following factors: gestational age (<32 weeks or ≥32 weeks) at randomization, presence/absence of gestational diabetes, and highest sBA before randomization (<40 µmol/L, ≥40 µmol/L to <100 µmol/L, or ≥100 µmol/L) after confirmation of study eligibility. Participants with highest pre-randomization sBA <40 µmol/L shall comprise no more than 33% of the primary cohort for Part 1 and Part 2, respectively.
  - For Part 1, in a 1:1:1 ratio via a computer-generated randomization schedule to receive volixibat 20 mg BID, volixibat 80 mg BID, or placebo BID
  - For Part 2, in a 1:1 ratio via a computer-generated randomization schedule to receive the selected volixibat dose (determined at the interim analysis) or placebo BID
- For the supplemental cohort, participants will be randomized with stratification (based on gestational age at randomization and presence/absence of gestational diabetes) after confirmation of study eligibility in a 1:1 ratio via a computer-generated randomization schedule to receive volixibat 20 mg BID or 80 mg BID.

Efficacy endpoints will be evaluated using stratification factors as covariates or stratification variables for analyses, as specified in [Section 6](#). If there is an imbalance in presumed prognostic baseline characteristics between treatment groups, efficacy evaluations may be performed that include these baseline values in efficacy analysis models as covariates; these evaluations will be considered sensitivity analyses.

For efficacy endpoints, the baseline value of the efficacy variable(s) will be included as a covariate in the efficacy analysis model.

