### **3.4. Examination of Participant Subgroups**

Subgrouping of participants based on randomization stratification factors will be explored for subgroup analyses. If there is an imbalance between treatment groups in presumed prognostic baseline characteristics that are not stratification factors, subgroupings based on these imbalanced baseline characteristics will also be explored for analysis of the primary and secondary endpoints. The presumed prognostic baseline characteristics include the following:

- Age ( $\leq 35$  years and  $> 35$  years)
- Race/Ethnicity (Hispanic, White [not Hispanic], South Asian [not Hispanic], and Other)
- Baseline ItchRO: (4-7 and  $> 7-10$ )
- Prior history of ICP (Yes and No)

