### 6.3. Exploratory Efficacy Endpoints

The exploratory efficacy endpoints are defined in [Section 1.1.3](#).

Continuous endpoints will be summarized using descriptive statistics. A p-value will be computed for between treatment comparisons using a van Elteren (vE) test (van Elteren 1960). The Wilcoxon–Mann–Whitney (WMW) test (Mann and Whitney 1947; Wilcoxon 1945) is widely used nonparametric approach to compare two treatments. In the

presence of stratum factors such as gestational age or ItchRO(Obs) Score, the van Elteren test, a stratified WMW test, can be used to adjust for the stratification factors. It was shown by Qu et al. (2008) that vE test preserves the type I error rate regardless of the existence of the stratum effects, and is better than the WMW test when the stratum effects are large.

A non-strata adjusted 95% CI for the difference in means between treatment groups will also be presented. A test of equality of variances will be performed. If the null hypothesis that the variances are equal is rejected, then the 95% CI will be constructed using a Satterthwaite approximation. Otherwise, the variances will be pooled.

For categorical endpoints, the number and percent for each category will be displayed. For responder-type analyses, within a treatment group, an approximate 95% CI will be presented using a stratified Wilson confidence interval (Yan and Su 2010). A 95% CI comparing two treatment groups based on stratum-adjusted MH proportions as described in Section 6.2 will also be generated. A stratified CMH test will be used to calculate the p-value for the difference between treatment groups. The method is applicable to the following endpoints:

- Proportion of participants with an early term delivery (37–38 weeks 6 days, inclusive)
- Proportion of participants with a full-term delivery ( $\geq 39$  weeks)
- Proportion of participants experiencing a perinatal death
- Proportion of participants with a spontaneous preterm delivery
- Proportion of participants with an iatrogenic preterm delivery attributable to ICP
- Proportion of neonates requiring neonatal intensive care unit (NICU) admission for  $\geq 12$  hours between birth and hospital discharge
- Proportion of neonates with meconium-stained amniotic fluid at delivery
- Proportion of participants requiring rescue medication for ICP
- Proportion of neonates with Apgar score  $< 7$  at 5 minutes of life
- Proportion of neonates with umbilical cord pH  $< 7.0$  at birth

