multiple imputation analysis for shift parameters 40, 41, ..., 50*/

%MIPARMS (DATA=XXXX, SMIN=40, SMAX=50, SINC=1, OUTPARMS=PARM2);
/*The following statements display the p-values that are associated with
the shift parameters.*/
PROC PRINT LABEL DATA=PARM2;
VAR SHIFT PROBT;
TITLE 'P-VALUES FOR SHIFT PARAMETERS';
LABEL PROBT='PR > |T|';
FORMAT PROBT 8.4;
RUN;
```

A sample of the SAS code for van Elteren test is provided as below:

```
proc nparlway data=adef ;  
  strata BLGSTAGE BLITCHRO BLGDIAB;  
  class trt01p;  
  var chg;  
run;
```

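### SAP 6.2 stratifies the composite outcome's risk difference on baseline ItchRO instead of highest sBA, leaves the confirmatory CMH strata unnamed, uses an SE that fails in sparse strata, and ties the endpoint to Week 3

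*SAP*

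**What the plan says.** SAP 6.2, item 2, tests the composite perinatal outcome with a stratified CMH test and makes its p-value the basis of inference. That sentence names no strata, and neither does Protocol 10.4.1.3. The next paragraph of SAP 6.2 adds a stratum-adjusted MH difference in proportions with a 95% CI, "where stratification factors include gestational age, baseline ItchRO score, and gestational diabetes", and indexes the strata from 1 to 12. The SE has n1h − 1 and n2h − 1 as denominators.

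Other places bear on this:

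- SAP 3.3 allocates by minimisation on gestational age, "presence/absence of gestational diabetes, and highest sBA before randomization". Protocol 6.3.1 repeats these three factors for Part 2.
- SAP 3.3 also sets a general rule: "Efficacy endpoints will be evaluated using stratification factors as covariates or stratification variables for analyses, as specified in" Section 6.
- SAP 3.4 lists baseline ItchRO, split into 4–7 and >7–10, under "presumed prognostic baseline characteristics that are not stratification factors".
- SAP 6.3 introduces the van Elteren test in the "presence of stratum factors such as gestational age or ItchRO(Obs) Score", and the sample code in SAP Appendix 3 has "strata BLGSTAGE BLITCHRO BLGDIAB".
- SAP 6.2 and Protocol 10.4.1.3 both summarise composite responders at Week 3. SAP 1.1.2 defines the composite by preterm delivery before 37 weeks, neonatal unit admission between birth and discharge, fetal death after randomisation, and neonatal death within 28 days of birth.

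**The concern.** The composite is third in the fixed testing sequence (SAP 3.5, Protocol 10.4.1.2), so its test should be fully determined before unblinding. It is not. The general rule in SAP 3.3 points to the randomisation factors but defers to Section 6, where the only list given contains ItchRO. Two analysts could defend different CMH strata, and the choice could be made after seeing data.

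The listed set also leaves out the factor with the strongest stated rationale. Protocol 2.2.1 justifies the primary endpoint with the words "Given the evidence supporting the role of elevated sBA as a driver of adverse perinatal outcomes". The ItchRO list may be carried over from another plan. SAP 6.3 refers to the observer version of ItchRO, which the protocol mentions only for another study, where "decreases in both sBA and ItchRO (observer) were observed at Week 2 and continued to decline even further at Week 4 in pediatric participants". This trial uses the Adult ItchRO.

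Two further defects sit in the same item. The planned CI can fail to compute, and a literal Week 3 cut would drop events that the definition counts.

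**Working it through.** **1. Number of strata.** The SAP's own figure is 12.

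- Factors listed in SAP 6.2, with the only ItchRO categories defined (SAP 3.4): 2 × 2 × 2 = 8. This does not reproduce 12.
- Randomisation factors (SAP 3.3, Protocol 6.3.1): 2 × 2 × 3 = 12. This matches.
- If the list is read as non-exhaustive and sBA is added: 2 × 2 × 2 × 3 = 24.
- Twelve strata with ItchRO would need a three-level ItchRO, which neither document defines.

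**2. Effect of the choice on the CMH test.** The documents give no composite event rate, so rates are assumed across the three sBA levels. Settings: 200 participants; minimisation (probability 0.8) on the three Part 2 factors; gestational age <32 weeks 30%, gestational diabetes 20%, sBA levels 33/45/22%, high ItchRO 40%; 3000 trials per cell (Monte Carlo SE about 0.9 points for power, 0.4 for type I error). Rejection rates are shown at treatment risk ratio 1 / 0.6 / 0.5:

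| Event rates by sBA | ItchRO risk ratio | 12 randomisation strata | 8 ItchRO strata |
|---|---|---|---|
| 10/25/60% | 1.0 | 0.045 / 0.503 / 0.717 | 0.030 / 0.462 / 0.676 |
| 10/25/60% | 1.5 | 0.056 / 0.512 / 0.727 | 0.034 / 0.477 / 0.698 |
| 15/25/45% | 1.0 | 0.051 / 0.458 / 0.643 | 0.047 / 0.443 / 0.644 |
| 15/25/45% | 1.5 | 0.049 / 0.454 / 0.656 | 0.041 / 0.450 / 0.658 |
| 20/25/35% | 1.0 | 0.043 / 0.420 / 0.631 | 0.045 / 0.414 / 0.629 |
| 20/25/35% | 1.5 | 0.046 / 0.425 / 0.629 | 0.045 / 0.435 / 0.632 |

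Power lost with ItchRO strata, by subtraction: 2.9 to 4.1 points in the steep case (for example 0.727 − 0.698 and 0.503 − 0.462), −0.2 to 1.5 in the middle case, and −1.0 to 0.6 in the flat case. Type I error with ItchRO strata is 3.0% to 4.7%, so the test is conservative when sBA is strongly prognostic and is not inflated.

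A second simulation (rates 20/35/60%, risk ratio 0.6, five sets of stratum shares, 1500 trials each) counted disagreements. Significance at 0.05 differed between the 12- and 8-strata tests in about 6–8% of trials, and among the 8-, 12- and 24-strata versions in about 11–12%.

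**3. The SE.** Each stratum contributes w² × [p1*(1 − p1*)/(n1h − 1) + p2*(1 − p2*)/(n2h − 1)]. With n1h = 1 (no event) and n2h = 3 (one event):

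- w = (1 × 3)/(1 + 3) = 0.75
- p1* = 0.5/2 = 0.25 and p2* = 1.5/4 = 0.375
- the first term is 0.25 × 0.75 / 0, which is undefined.

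With n1h = 0 the weight is 0, and it is the stratum difference that is 0/0.

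Such cells are plausible. With gestational age <32 weeks 30%, gestational diabetes 15% and sBA ≥100 20%, the smallest of the 12 cells expects 100 × 0.30 × 0.15 × 0.20 = 0.9 participants per arm. Simulated chance that some stratum makes the SE undefined:

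| Assumed stratum shares | 12 strata | 8 strata |
|---|---|---|
| 36 sets (gestational age <32 weeks 20/30/40%, gestational diabetes 10/20/30%, sBA ≥100 10/25%, sBA <40 33%, high ItchRO 30/50%) | 43–95%, median 84% | 4–79%, median 54% |
| Four uneven sets in the second simulation | 78–89% | 33–67% |
| Near-equal strata | about 1% | 0% |

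**4. Week 3.** Part 2 entry runs from 20w0d to 36w0d (Protocol 5.1), a span of 16 weeks. Week 3 falls before 37w0d for anyone randomised before 37 − 3 = 34w0d, which is 14 of those 16 weeks of eligibility. These participants can have a qualifying preterm delivery after Week 3. The admission and neonatal death components can also fall after Week 3 in anyone who delivers later than that.

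**The case against.** The best defence is that the CMH strata are less open than they look. SAP 3.3 gives a general rule, the randomisation factors give 12 cells, SAP 6.2 indexes 12, and the ItchRO list is attached to the supplementary difference and CI rather than to the CMH sentence. That supports the proposed correction, but it does not settle the test, because SAP 3.3 defers to Section 6 and the only list there says something else. The count of 8 also rests on the subgroup cut-points in SAP 3.4, since SAP 6.2 gives none.

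Other objections stand as limits:

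- The power effect is within simulation noise, or nearly so, at two of the three assumed gradients.
- The supportive logistic regression already adjusts for baseline sBA.
- The SE problem touches the CI, not the CMH p-value. Its frequency depends on stratum shares that the documents do not give, apart from the 33% cap on sBA <40 in SAP 3.3.
- Moving to 12 strata makes that SE problem more frequent, so the swap needs a companion change.
- A careful analyst would probably follow the endpoint definition rather than truncate at Week 3. The 14-of-16-weeks figure describes eligibility, not enrolment. Protocol 4.3.2.1 expects participants towards the upper end of the gestational range and cites a trial with median 34.4 weeks at randomisation.

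None of these removes the contradictions in the text.

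**Conclusion.** The point holds and should be fixed before unblinding. Three things are established by reading alone: the factors listed in SAP 6.2 conflict with its 12 strata and with SAP 3.3 and 3.4; the strata of a confirmatory test are not named; and the Week 3 summary contradicts the endpoint definition. That the SE is undefined with one participant in an arm of a stratum follows from the formula.

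The size is moderate and rests on assumptions. ItchRO strata would cost about 3 to 4 points of power if sBA is strongly prognostic and about none otherwise, with no inflation of type I error. The chance that the CI cannot be computed runs from about 1% with near-equal strata to 95% in the most uneven set examined. The share of events that a Week 3 cut would lose cannot be derived from the documents.

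The SAP states that it is based on Protocol Version 1, but the strata conflict is internal to the SAP and the Part 2 randomisation factors are the same in the current protocol.

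**What to change.** In SAP 6.2, state that the CMH test and the MH difference with its CI are both stratified by the Part 2 randomisation factors: gestational age (<32, ≥32 weeks), gestational diabetes (present, absent) and highest sBA before randomisation (<40, 40 to <100, ≥100 µmol/L). Align SAP 6.3, which reuses the interval for ten binary exploratory endpoints, and the van Elteren code in Appendix 3.

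Replace the SE with an MH risk-difference variance that remains valid in sparse strata, such as Sato's, or prespecify a rule for pooling strata. In 16,000 simulated trials with the 12 strata, the Sato interval was always defined and its coverage was 94.8% to 95.7%.

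In SAP 6.2, Protocol 10.4.1.3 and the matching synopsis text, drop Week 3 for the composite. Say instead that each component is counted over its own window: delivery before 37 weeks; neonatal unit admission from birth to hospital discharge; fetal death after randomisation, or neonatal death to 28 days after birth.

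The cost is wording and one variance formula or pooling rule. All variables are already collected for randomisation. The protocol edit would need IRB/IEC approval as an amendment (Protocol 11.1), so it is best combined with the next one.
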